#### Study Interventions and Measures:

In this intervention, parent-infant dyads randomized to the digital arm will receive developmentally appropriate e-books. Those randomized to the standard arm will receive developmentally appropriate board books. Participants will receive either the e-book or board book for their 6, 9 and 12 month well visits. The developmentally appropriate books selected for each of the 3 well visits are as follows: [name] *Hop on Pop* for the 6 month well visit, Sandra Boynton's *Barnyard Dance* for the 9 month well visit, and Margaret Wise' *Goodnight Moon* for the 12 month well visit.

In addition to the books, parent-infant dyads in both arms will be provided information on the importance of early parent-child reading activity by pediatric clinicians using the Reach Out and Read framework.

We will collect standard measures of demographics (child age, sex, race/ethnicity, maternal age, family structure, maternal education level, and family income category), maternal adversity (9 ACE questions), maternal health literacy (SAHL), and maternal depressive symptoms (EPDS) at baseline. About 1 month after the infant has, or is age-eligible for, their 6 and 9 month well visits we will collect measures of reading activity (StimQ and ERPQ). Roughly 1 month after the infant has, or is age eligible for, their 12 month well visit, the infant will receive a developmental assessment (BSID-III), along with additional measures of reading activity (StimQ, ERPQ). They will additionally complete the paper-based DialogPR-I at this visit. A video recorded reading task will be obtained for up to 40 participants. These participants will be asked preliminary questions about their reading practices at home at the time of the video session.

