Electronic or e-books for children have grown in popularity. They come in a number of formats including Nooks, Kindles, and iPads as well as a number of digital apps that are used on smart phones and tablets. They permit children to follow along with stories, activate games and sounds, and listen to music. Their popularity may be related to parental beliefs that e-books help promote child intellectual development. However, a recent study examining reading behaviors and comprehension among children using e-books found that e-books were associated with fewer dialogic language behaviors and lower reading comprehension compared to traditional books. However, the study was limited by only enrolling middle to upper income preschool-aged children, so it isn't clear that the findings are generalizable to younger children from low-income households.

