### **3.2 Allocation to Treatment Groups and Blinding**

Participants will be stratified by clinic site and randomized to receive literacy promotion using 1) standard early reader board books or 2) digital electronic early reader e-books. Randomization sequences will be developed by the study team using computer-generated random numbers prior

to study enrollment and will be placed in sealed opaque envelopes, assigning participants to one of the two treatment arms.

Participants in the video sub-study will also be randomized to determine the order in which they are asked to read the three versions of the selected book (print, basic e-book, enhanced e-book). As with the larger trial, randomization sequences will be developed by the study team using computer-generated random numbers prior to study enrollment and will be placed in sealed opaque envelopes, assigning participants to receive one of the six possible orders of the three book types.

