#### **5.1.4 Reading Activity (StimQ)**

The StimQ is an office measure of cognitive stimulation at home available in Spanish and English, and the Read subscale of the StimQ contains questions on the frequency of parent-child reading activity and the number and variety of books at home. Psychometric analysis of the StimQ shows high internal consistency (Cronbach's Alpha=0.89) and test-retest reliability ( $r=0.84$ ) and moderate correlation with the Bayley Scales of Infant Development ( $r=0.52$ ,  $p<0.001$ ).

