### 6.3 Statistical Methods

Summary statistics will be obtained, and differences between digital and standard arms will be assessed using intention-to-treat analysis. Cross-sectional differences in StimQ scores between digital and standard groups at the 6, 9 and 12 month well visits will be assessed using t-tests. To determine how the effects of digital versus standard literacy is associated with language development, we will develop regression models using longitudinal data methods that adjust for correlation in BSID-III scores over time and for potential confounding by demographic characteristics. To explore the impact of digital literacy on healthcare utilization, the EHR will be reviewed to identify a subjects' number of well visits and their vaccination history.

To determine whether parent adversity, health literacy, and/or parent mental health modify the effects of digital versus standard literacy on language development, we will develop similar regression models using longitudinal data methods, but we will also fit interaction terms between study group and ACE score ( $\geq 4$ ), SAHL (high or low) and EPDS score ( $> 10$ ). To determine if parent-child reading activity mediates the association of intervention group assignment and language development, we will use mediation analysis with separate models regressing group assignment on language development, parent-child reading activity on group assignment, and group assignment on language development adjusted for parent-child reading activity.

Assuming a mean cognitive subscale on the BSID-III of 96, a power of 0.70, an alpha of 0.05, and a clinically significant difference of 7.5 points on the BSID-III between groups, we estimate that we will need to recruit a total sample size of 100 eligible children (50 in each group) to participate in the main RCT study (Figure 1). To attain thematic saturation in the Video Sub-study, we will recruit up to 40 participants 9-12 months of age. These 40 participants may be recruited external to the main study if we are unable to recruit up to 40 from the 100 enrolled in the main study in a timely fashion. All analyses will be conducted using Stata Statistical Software, version 13 (College Station, TX).

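### No covariates are named for the mediation models, so where book format changes reading, shared causes of reading and language bias the indirect effect, and the direct effect oppositely

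*Combined protocol and SAP*

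**What the plan says.** Section 6.3 describes three sets of regression models, and they differ in what is said about adjustment.

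- **Main language model.** It is to "adjust for correlation in BSID-III scores over time and for potential confounding by demographic characteristics".
- **Effect-modification models.** Here "we will develop similar regression models using longitudinal data methods, but we will also fit interaction terms" with ACE, SAHL and EPDS. The word *similar* carries the main model's adjustment over.
- **Mediation models.** There are three: language and group, then "parent-child reading activity on group assignment, and group assignment on language development adjusted for parent-child reading activity". I read them in the usual direction, with group as the predictor. The only terms named are group, reading activity and language. Nothing refers back to the main model's covariates.

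Section 3.2 makes clear what is assigned: "Participants will be stratified by clinic site and randomized to receive literacy promotion using" board books or e-books. Reading activity is measured afterwards. Under Study Interventions and Measures, the Abstract lists demographics (including maternal education, family structure and income category) together with "maternal adversity (9 ACE questions), maternal health literacy (SAHL), and maternal depressive symptoms (EPDS) at baseline". In 6.3 the last three appear only as effect modifiers. The plan states no assumption about unmeasured confounding of the mediator and no sensitivity analysis for it.

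**The concern.** Randomisation protects the comparison of arms on reading and on language. It does not protect the association between reading and language within arms. Parents who read more may also differ in education, health literacy, depressive symptoms or adversity, and each of these could affect the child's language by another route.

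The plan names adjustment for confounding in the randomised comparison, where none is needed to remove bias. It names none for the one path that is observational. Run as written, the models could credit or deny reading a role in carrying the effect of book format, with a matching error of opposite sign in the direct effect. The variables that would reduce this error are already being collected.

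**Working it through.** **The plan's own figure.** The documents state no figure for the mediation analysis. The sample size fixes the scale. With a difference of 7.5, SD 15 (Figure 1), two-sided alpha 0.05 (sidedness assumed) and power 0.70:

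n per arm = 2 × (1.960 + 0.524)² × 15² / 7.5² = 8 × 6.17 = 49.4, so 50 per arm and 100 in total.

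This matches 6.3. The 80 and 90 in Figure 1 also reproduce.

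**Bias formula.** Let a be the effect of format on reading (in SD of reading), b the true effect of reading on language, c′ the true direct effect, and δ the bias in the reading-to-language coefficient. In linear models:

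- estimated indirect effect = a × (b + δ), a bias of a × δ
- estimated direct effect = c′ − a × δ, the opposite bias
- the total effect is unchanged, because format is randomised

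If δ has the same sign as b, mediation is exaggerated. If the signs differ, it is shrunk or hidden. If a = 0, the mean bias is zero whatever δ is.

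**Inputs for an illustration.** SD 15 and n = 100 come from the plan. Three things are assumed: b = 0; values of a from 0 to 0.8 SD; and a within-arm correlation r between reading and BSID-III that arises wholly from shared causes. Then δ = 15 × r, and the bias in the indirect effect is 15 × r × a points:

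| r | a = 0 | a = 0.2 | a = 0.5 | a = 0.8 |
|---|---|---|---|---|
| 0.10 | 0 | 0.30 | 0.75 | 1.20 |
| 0.26 | 0 | 0.78 | 1.95 | 3.12 |
| 0.30 | 0 | 0.90 | 2.25 | 3.60 |
| 0.40 | 0 | 1.20 | 3.00 | 4.80 |

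**Simulation check** (50 per arm, 2,500 to 4,000 runs per setting). *False mediation* means that both path tests are significant although b = 0.

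- r = 0.10: mean indirect effect −0.01, 0.30, 0.75 and 1.21 points at a = 0, 0.2, 0.5 and 0.8; false mediation 0.6%, 2.8%, 12% and 16%.
- r = 0.30: −0.01, 0.90, 2.22 and 3.56 points; false mediation 4.5%, 15%, 59% and 83%.
- r = 0.26: about 0 points and 3.6% at a = 0; 0.77 points and 13% at a = 0.2; about 2.0 points and 51% to 52% at a = 0.5.
- r = 0.40, a = 0.8: 4.78 points and 96%.

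At nonzero a, the direct effect was biased by about the same amount with the opposite sign.

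**Effect of adjustment.** In the settings run with r = 0.10 and 0.30, entering the shared cause in both models brought the mean indirect effect to within 0.03 points of zero and false mediation to between 0.2% and 5.3%. Covariates that capture only half of its variance remove less. At a = 0.5 and r = 0.26 the remaining bias is 0.5 × 15 × 0.13 / 0.87 = 1.12 points. Simulation gave 1.14 points, with false mediation in 25% of trials.

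**The case against.** **Silence is not exclusion.** Section 6.3 describes each mediation model by its core terms, and the same section commits to demographic adjustment elsewhere. This stands in part: the claim can only be that no covariates are named. But the sentence lacks the linking phrase used for the effect-modification models. Implied demographics would in any case leave out ACE, SAHL and EPDS.

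**The bias is conditional.** A reader might infer that any shared cause of reading and language will surface as an effect of book format through reading. The documents do not support that. Because format is randomised, a shared cause enters the indirect effect only when multiplied by a. Both arms receive the same three titles and the same clinician advice (3.1.1 and 3.1.4), so a small a is plausible. At a = 0.1 and r = 0.26 the bias is about 0.4 points, with false mediation in about 5% of trials. Against this, mediation is of interest mainly if format does change reading, and that is when the bias arises.

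**The size rests on assumptions.** The documents give neither a nor the strength of confounding. Section 5.1.4 reports a "moderate correlation with the Bayley Scales of Infant Development" of 0.52 for the StimQ, and a reader might take that as the amount of confounding. It is a scale-validity correlation, and the reading measure is only a subscale. The 0.26 used above is half of it, an arbitrary choice. Recruiting only Medicaid families may also narrow the socioeconomic differences. All of this stands, which is why a range is shown.

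**The analysis is secondary.** Mediation appears in no aim (2.1, 2.2) and no endpoint (6.1, 6.2). This also stands, and it limits the weight of the point.

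**Conclusion.** The concern holds in a limited form. The mediation models name no covariates, and reading is not randomised. Where format changes reading, running the models as written biases the indirect effect by a × δ and the direct effect by −a × δ.

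Under the assumptions above, the size runs from nothing (a = 0), through about 0.3 points (a = 0.2 SD, r = 0.10) and about 2 points (0.5 SD, 0.26), to about 5 points (0.8 SD, 0.40). The 7.5-point planning difference gives a sense of scale only, since it was set for the total difference between arms on the cognitive subscale. The direction is not fixed: mediation can be created or concealed.

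The primary comparison and the total effect of format are unaffected. The change is worth making because the models as stated give a worse answer than ones the trial can fit with data already planned.

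**What to change.** In 6.3, enter the same pre-specified baseline covariates in the reading model and in the language model that contains reading:

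- clinic site, child age and sex
- maternal education, family income category and family structure
- ACE, SAHL and EPDS, using the baseline EPDS and not the one repeated at the second visit
- baseline reading activity, if collected. Section 3.1.4 says that it is, but the baseline lists in the Abstract, 3.1.3.1 and 4.1 omit it. These need to be reconciled.

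State the no-unmeasured-confounding assumption. Report how the indirect effect changes with the residual reading-language correlation, without a pass/fail threshold. The estimate reaches zero once the assumed correlation equals the observed within-arm one, so a fixed cut-off could reject a genuine effect. Describe the result as exploratory.

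**Cost.** SAP wording and a short extra analysis, with no new data. With two terms for site and one for each of the other eight, the list uses 10 degrees of freedom. Baseline reading makes 11, and categorical coding could bring it to about 15. That comes out of 100 − 3 = 97 before any dropout, and the interval may widen slightly. The covariates remove only the confounding they capture, so the sensitivity analysis is still needed alongside them.

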Participants in both study arms will be followed every 3 to 4 months until the infants are between the ages of 12 and 18 months, 30 days. Information on reading activities and developmental outcomes will be collected in concert with scheduled well child visits. Differences in reading activities and developmental outcomes will be assessed between groups using intention-to-treat analysis. Parents will complete measures of demographics, health literacy, and maternal depressive symptoms at baseline. Parents will also complete measures of reading activity with their infant about 1 month after the child has, or is age-eligible for, their 6, 9, and 12 month well visits. The infant will also receive a developmental assessment at the second study visit which will happen about 1 month after they have, or are age-eligible for, their 12 month well visit. At this time the infant should be between 12 and 18 months, 30 days old. Secondary data to address these study questions does not exist, which will necessitate the collection of new data as proposed here. We anticipate that this collection of rich new data will support a careful assessment of the effects of digital vs. standard literacy promotion. The HER will be reviewed for children in both arms to count the number of well child visits and examine their vaccination history.

We anticipate collecting this data in conjunction with well child visits. In our experience, low-income families can be difficult to reach for study visits, even with appropriate study incentives. By coordinating data collection with the 6, 9, and 12 month well child visits timeframes, we can increase the probability of families attending both the well visits (to receive the Reach Out and Read Program materials) and the study visits (to collect measures of reading activity and development). In a previous study of 2100 children enrolled in a study of developmental screening, we were able to achieve a >90% follow-up rate by coordinating data collection with well child visits. In addition, our research staff can check the clinic schedule to ensure families have made timely well child visit appointments and then make reminder calls to families prior to these visits to encourage parents to attend. Study visits will be held at a location that is preferred

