### **3.3 Study Duration, Enrollment and Number of Sites**

#### **3.3.1 Duration of Study Participation**

The study duration for the randomized control trial per subject will be approximately 7 months following enrollment. The study duration for the video sub-study will be one day of participation.

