#### **3.3.2 Total Number of Study Sites/Total Number of Subjects Projected**

The randomized control trial will be conducted at three CHOP Care Network Practices: 1) Roxborough, located in Philadelphia, Pennsylvania, 2) Indian Valley located in Souderton, Pennsylvania and 3) Cobbs Creek, located in Philadelphia, Pennsylvania. These sites have been individually recruited to participate (see PeRC letter of support) and have agreed to participate.

Recruitment for the randomized control trial will stop when approximately 100 subjects (100 dyads of parent and infant) are enrolled. Recruitment for the video-taped component will stop when approximately 40 participants have completed the video and interview task.

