### **6 STATISTICAL CONSIDERATIONS**

#### **6.1 Primary Endpoint**

The primary endpoint for the randomized control trial will be the BSID-III scores at the second study visit when the child is between 12 and 18 months, 30 days of age.

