**Figure 1**

Power	n
0.60	80
0.65	90
0.70	100

Assuming a mean cognitive subscale of the BSID-III, an alpha of 0.05, and an SD of 15.

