## **8.4 Recruitment Strategy**

### **8.4.1 Randomized Control Trial**

We will have an EHR recruitment prompt sent only to potentially eligible children with Medicaid at their 4 month well visit at the CHOP Primary Care Roxborough, PA, CHOP Primary Care Cobbs Creek and CHOP Primary Care Indian Valley. Parents who are conceivably interested in participating will be contacted by research staff. Research staff will briefly explain the study procedures, guided by the information set forth in the approved consent form. This includes reading the inclusion criteria to the potential participant, and asking whether or not this individual is interested in participating. Research staff will then schedule a time to meet with the parent in person. This will happen at a time before their infant's 6 month well visit in order to obtain informed consent, confirm that all of the inclusion criteria are met, and randomize the

participant into either the digital or standard book group. In the event that the research staff is unable to confirm that all inclusion criteria are met after the participant has been enrolled, the participant will no longer be able to participate. Additionally, potentially eligible 5 to 7 month olds that have been identified by study staff on EPIC as potentially eligible by screening via review of the medical record, may be approached in person before or at the time of their 6 month well visit. These potentially eligible participants will be screened, consented and enrolled into the study prior to the child's time with the provider.

We may also hang recruitment flyers in the hallways at both clinics giving information about the study and contact information for the study coordinator in case they are interested and we miss their names in the screening process.

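### The stated power of 0.70 holds only if essentially all 100 recruited infants have an analysed BSID-III score; recruitment stops at about 100 with no allowance for loss

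*Combined protocol and SAP*

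**What the plan says.** Section 6.3 (Statistical Methods) assumes a BSID-III cognitive mean of 96, a difference of 7.5 points, alpha 0.05 and power 0.70, and concludes: "we estimate that we will need to recruit a total sample size of 100 eligible children (50 in each group"). Figure 1 lists n of 80, 90 and 100 for power 0.60, 0.65 and 0.70, with "an alpha of 0.05, and an SD of 15". Its n column does not say whether it counts infants enrolled or infants analysed.

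Section 3.3.2 sets the stopping rule: "Recruitment for the randomized control trial will stop when approximately 100 subjects (100 dyads of parent and infant) are enrolled". In the same section, recruitment to the video sub-study is tied to participants who have finished the task.

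On timing, section 6.1 says "The primary endpoint for the randomized control trial will be the BSID-III scores at the second study visit", and section 3.3.1 says "The study duration for the randomized control trial per subject will be approximately 7 months following enrollment".

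On retention, section 3.1.1 acknowledges that low-income families are hard to bring back for visits even with incentives. It then cites an earlier study in which "we were able to achieve a >90% follow-up rate by coordinating data collection with well child visits". That rate does not enter the sample-size calculation. Section 8.4.1 also ends participation where staff are "unable to confirm that all inclusion criteria are met after the participant has been enrolled".

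**The concern.** A sample-size formula returns the number of outcomes needed in the analysis. If that number is also the recruitment target and the point at which enrolment stops, the design power is reached only when nobody is lost. Here the outcome is a single examiner-administered assessment at the last visit, so an infant who misses that visit contributes no observed primary outcome. The protocol does not claim complete follow-up, and section 6.3 names intention-to-treat without a method for missing BSID-III scores.

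What is at stake is how a null result is read. The abstract asks whether e-books work as well as board books, so a finding of no difference is a plausible outcome. Readers would take the risk of having missed a 7.5-point difference as the 30% implied by section 6.3, when the actual risk is higher by an amount that depends on follow-up.

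**Working it through.** **Inputs.** Difference 7.5, alpha 0.05 and power 0.70 (section 6.3); SD 15 (Figure 1); 1:1 allocation (Abstract). Standardised difference d = 7.5/15 = 0.5. The mean of 96 does not enter the calculation. The documents do not state sidedness. Two-sided is inferred, because a one-sided test would need 58, 66 and 76 for the three rows.

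**Step 1: reproduce Figure 1.** Normal formula, total N = 4(1.960 + z)²/d² = 16(1.960 + z)², where z is the normal quantile of the power:

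| Power | Normal formula | Rounded up per arm, total | t-test | Figure 1 |
|---|---|---|---|---|
| 0.60 | 78.4 | 80 | 80.3 | 80 |
| 0.65 | 88.0 | 90 | 90.0 | 90 |
| 0.70 | 98.8 | 100 | 100.7 | 100 |

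All three rows are matched with no inflation for loss, so n in Figure 1 is the number analysed. The printed figures are correct for that meaning.

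**Step 2: power when fewer than 100 are analysed.** Normal power = Φ(d√N/2 − 1.960). At 100 this is Φ(2.500 − 1.960) = 0.705; at 90 it is Φ(2.372 − 1.960) = 0.660. The t-test values use the noncentral t distribution.

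| Analysed | t-test | Normal |
|---|---|---|
| 100 | 0.697 | 0.705 |
| 98 | 0.688 | 0.697 |
| 95 | 0.674 | 0.683 |
| 92 | 0.660 | 0.669 |
| 90 | 0.650 | 0.660 |
| 80 | 0.598 | 0.609 |

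The 90 row is the lower limit of the follow-up rate cited in section 3.1.1. The 80 row is an assumption: no document gives a 20% loss. It is shown because Figure 1 already has a row at that n.

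**Step 3: precision and detectable difference.** The 95% confidence interval half-width is t(0.975, N−2) × 15 × √(4/N), which is 5.95 points at 100 and 6.28 at 90, or 0.33 wider. The difference detectable with power 0.70 is (1.960 + 0.524) × 15 × √(4/N) by the normal formula: 7.45 points at 100 and 7.86 at 90. The t-test gives 7.94 at 90.

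**Step 4: possible gain from covariate adjustment.** Section 6.3 plans to adjust for demographic characteristics, but the documents give no R². Taking assumed values, the effect size becomes d/√(1 − R²). At 90 analysed:

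| Assumed R² | t-test | Normal |
|---|---|---|
| 0.05 | 0.672 | 0.682 |
| 0.10 | 0.696 | 0.705 |
| 0.15 | 0.721 | 0.730 |

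The plan's own calculation takes no credit for this gain.

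**The case against.** The strongest reply is that nothing is miscalculated and the effect is small. Figure 1 already shows 0.65 at 90 and 0.60 at 80, so an attentive reader can see what losing 10 or 20 infants costs. The only follow-up figure in the protocol is above 90%, obtained with the same approach of timing data collection to well visits. This trial adds reminders, locations chosen by the parent, a wide age window for the final visit and a $40 final payment. If that rate is repeated, the cost is under 5 percentage points and the confidence interval widens by no more than about a third of a point. The choice between the t-test and the normal formula moves power by about as much as losing two infants. Covariates explaining 10% of the variance would bring power at 90 analysed back to about 0.70.

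Most of this stands, and it limits the weight of the point. It does not remove it. Figure 1 does not say that its n counts completers, and section 6.3 attaches 0.70 to the number recruited. The earlier follow-up rate comes from another study and is not adopted as an assumption here. The retention measures reduce loss but do not make it zero.

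The section 8.4.1 removals are weak support. Section 6.3 speaks of eligible children, and a child removed because eligibility cannot be confirmed may not be meant to count towards the 100. The documents give no rate and do not say whether such a child is replaced. The conclusion does not depend on them.

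**Conclusion.** The concern holds as a minor one. The arithmetic in Figure 1 is right for infants analysed; the fault is using that number unchanged as the number to recruit. There is almost no slack: with two infants lost, power is below 0.70 by either formula, and by the t-test it is 0.697 even with all 100. At 90 analysed, power is 0.65 to 0.66 and the risk of missing 7.5 points is 34-35% rather than 30%. Follow-up above 90% would cost less than that, and 80 analysed would raise the risk to 39-40%.

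These figures rest on the plan's difference and SD, an inferred two-sided test, equal arms after loss, and no credit for covariate adjustment.

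**What to change.** Label the n column of Figure 1 as infants analysed, and replace the unconditional statement in section 6.3 with one along these lines: *Recruiting 100 gives power of about 0.70 only if all complete the BSID-III; about 0.65 if 90 complete (higher if follow-up exceeds 90%) and about 0.60 if 80 complete, before any gain from covariate adjustment.* Stating there that the test is two-sided would remove the need to infer it.

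The cost is one sentence and a column label. Enrolment, budget and analysis are unchanged; the stated power simply becomes conditional on follow-up.
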